4.0 Study Endpoints

*4.1 Describe the primary and secondary **study** endpoints. See links below for discussion of study endpoints and how they may differ from study objectives. These are most common in clinical trials but are sometimes applicable to other types of biomedical research, as well as social, behavioral, or educational research. See link below for a discussion.*

https://docs.google.com/document/d/1Wocz7K7a0hCQJPPO_khh511SQjhGDDGHzcOPRHR5Tw/edit?usp=sharing

Delay discounting: Change in discounting rates will be compared within-subjects between pre intervention and post intervention. In addition, differences in discount rates will be compared between groups (EFT and CET).

Alcoholic Drinks: Change in drinks per day and number of positive breath alcohol samples (BrAC) will be compared within-subjects between pre intervention and post intervention. In addition, differences in drinks per day and number of positive BrAC samples will be compared between groups (EFT and CET).

Alcohol Demand: Change in demand for alcohol will be compared within-subjects between pre intervention and post intervention. In addition, differences in alcohol demand will be compared between groups (EFT and CET).

Alcohol Craving: Change in alcohol craving will be compared within-subjects between pre intervention and post intervention. In addition, differences in alcohol craving will be compared between groups (EFT and CET).

4.2 *Describe any primary or secondary safety endpoints. These should be included for all studies that are greater than minimal risk. (Minimal risk: The probability and magnitude of harm or discomfort anticipated in the research that are not greater in and of themselves than those ordinarily encountered in daily life or during the performance of routine physical or psychological examinations or tests.):*

This study's procedures are not more than minimal risk.

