Primary hypotheses: Our primary measure of temporal window is delay discounting (DD). Our primary measure of alcohol consumption is self-reported drinks per day. Participants are asked to report how many standard drinks they had for the previous 24 hours on each day of the 7 day baseline and 28 day intervention period. Our secondary measure of alcohol consumption is breath alcohol samples from the remote breathalyzer. Participants will provide three breath samples daily for the 7 day baseline and 28 day intervention period. Our primary measures of demand are alpha and Q0. Alpha and Q0 are two derived outcomes from a hypothetical alcohol purchase task. Participants are asked to report the number of standard drinks they might hypothetically purchase at increasing price points. Q0 is a measure of how many drinks a participant might purchase when drinks are free (price = \$0). Alpha is a measure of the participants sensitivity to increasing prices (i.e., how quickly they decide to stop purchasing at higher prices). Our measure of craving is the Alcohol Urges Questionnaire (AUQ). Our measure of neural activity is BOLD response. We hypothesize that baseline BOLD response will be predictive of the efficacy of the intervention. We will model our primary outcome measures using a mixed-effects hierarchical model that includes day, time (pre/post intervention), and intervention group. A random effect will be included for each participant. We will include baseline BOLD response as a fixed-effect covariate in our analysis.

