Objective 1: *We hypothesize that an intervention involving EFT will increase the temporal window and decrease alcohol valuation (consumption, demand, and craving).*

Our primary measure of alcohol use during the intervention period will be the daily self-reported number of drinks per day and the SOBERLINK breathalyzer screens. We will use generalized linear mixed models to compare the daily number of drinks between the EFT and CET groups. Mixed models is a method suited to the analysis of repeated measurement data. Here, the daily number of drinks will be modeled using a Poisson distribution. In the event the daily number of drinks exhibit over dispersion, other distributions, such as a negative binomial, will be considered. In a similar manner, dichotomous breathalyzer results data (positive or negative) throughout the 5-week field test will be analyzed as a function of intervention assignment, while accounting for time of day (morning, afternoon, evening) and repeated measures from each subject. Intrasubject correlation will be accounted for using an autoregressive correlation structure (AR(1)), since drinking days may be temporally related. In the event the AR(1) correlation structure is not representative of the data, other correlation structures will be considered. All missed assessments, although rare in our experience with similar field studies (approximately 5%), will be included as missing data. In the event of high rates of missing data, we will employ techniques consistent with the intention-to-treat paradigm, such as last observation carried forward methods or worst-case scenario (that all missing data is a positive BrAC measure).

Secondary analyses. In addition to the primary hypotheses listed above, we propose several additional analyses that will more fully characterize the behavior of our research participants and potentially lead to future research questions related to EFT in AUD. To this end, we hypothesize that EFT will result in changes (baseline versus post-intervention) in secondary outcome measures (e.g., Alcohol Withdrawal Symptoms Checklist). All these secondary hypotheses will be analyzed analogous to the primary hypothesis.

Covariate Plan:

We will test for individual differences in outcome measures for the intervention for each of these stratified variables. Therefore, we will include AUDIT score, SES, age, and gender in the analyses testing for an interaction between these variables and the intervention.

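### The daily-drinks model names no participant-level pre/post effect, so if people change by different amounts its tests of change have standard errors that are too small

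*Protocol*

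**What the plan says.** - **Endpoint.** Protocol 4.1: "Change in drinks per day and number of positive breath alcohol samples (BrAC) will be compared within-subjects between pre intervention and post intervention". It also lists a comparison of drinks per day between EFT and CET.
- **Protocol model.** Section 5.2 specifies a "mixed-effects hierarchical model that includes day, time (pre/post intervention), and intervention group", then "A random effect will be included for each participant". Baseline BOLD response enters as a fixed covariate. No group-by-time term is written. Drinks are reported "on each day of the 7 day baseline and 28 day intervention period".
- **SAP model.** Under Statistical Analyses, Objective 1: "We will use generalized linear mixed models to compare the daily number of drinks between the EFT and CET groups". The SAP adds that "the daily number of drinks will be modeled using a Poisson distribution", with a negative binomial as one alternative if counts are over-dispersed.
- **Correlation.** The same paragraph says: "Intrasubject correlation will be accounted for using an autoregressive correlation structure (AR(1)), since drinking days may be temporally related". It then allows a change: "In the event the AR(1) correlation structure is not representative of the data, other correlation structures will be considered". It names no random effect and no pre/post term.
- **Level.** SAP, Statistical Principles, sets 5% for all analyses.
- **Sizing.** SAP, Sample size, sizes the trial on a group-by-time interaction with two groups and two measurements.

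**The concern.** A participant intercept removes stable differences in how much people drink. AR(1) removes carry-over that fades within days. Neither carries person-to-person differences in the shift from the baseline week to the intervention weeks. If those differences exist, the model treats them as day-to-day noise averaged over 35 reports, when they can only be averaged over participants.

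Some variation in change is to be expected. Participants enter wanting to quit or cut down (Protocol 12.2). They continue only after a baseline week with enough drinking (Protocol 8.2; SAP, Participant Retention). Protocol 5.2 itself hypothesises that baseline BOLD response predicts how well the intervention works, which means response is expected to vary.

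At stake are the confidence intervals and p-values for change in drinks per day, the primary consumption measure in Protocol 5.2. The breathalyzer model is exposed in the same way wherever a pre/post contrast is taken from it.

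**Working it through.** **1. The plan's own figure.** SAP inputs: f = 0.25, r = 0.5, alpha 0.01, two measurements. For the within-between interaction, λ = f² × N × 2/(1 − r). At N = 52, λ = 0.0625 × 52 × 2/0.5 = 13.0. The noncentral F on 1 and 50 df gives power 0.818; N = 50 gives 0.799. The stated 52 reproduces. The error term in that calculation is person-to-person variation in change, which the daily model as written leaves out.

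**2. The mechanism in closed form.** Let s be the day-to-day SD and t the SD of person-specific change. Ignore serial correlation and day.
- Variance of one person's change under a random intercept: s²(1/7 + 1/28) = 0.1786 s².
- True variance: 0.1786 s² + t².
- With s = 3 and t = 1.5 drinks (both assumed): 1.607 against 3.857. The SE ratio is √(1.607/3.857) = 0.645.
- Rejection rate: 2(1 − Φ(1.96 × 0.645)) = 20.6%.

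Both variances are divided by the number of participants, so the ratio does not depend on sample size. This shortcut runs slightly high because a fitted residual absorbs part of t². Refitting gives 18.2% for this case.

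**3. Large-sample calculation with AR(1) fitted.** The true 35-day covariance has an intercept (variance 0.5 to 1 times daily variance; the choice makes no material difference), a random pre/post change, and AR(1) with ρ from 0 to 0.4. The random-intercept-plus-AR(1) covariance that maximum likelihood converges to was found. With q = true/model-based variance of the contrast, the rate is 2(1 − Φ(1.96/√q)). All variances are assumptions.

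| Change SD ÷ daily SD | EFT-CET change test | Pre/post test, linear day included |
|---|---|---|
| 0 | 5.0% | 5.0% |
| 0.3 | 7.9-10.3% | 6.5-7.5% |
| 0.5 | 12.6-18.2% | 9-12% |
| 0.7 | 18.4-26.3% | 13-17% |
| 1.0 | 27-36% | 19-24% |

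Examples for the EFT-CET test: at 0.3 and ρ = 0.4, √q = 1.114, 1.96/1.114 = 1.759, rate 7.9%. At 0.7 and ρ = 0, √q = 1.752, 1.96/1.752 = 1.119, rate 26.3%. AR(1) does not rescue the test: with a true ρ of 0.2, the fitted value rises only to 0.23 and 0.26 at change SDs of 0.5 and 0.7. With s = 3, the range 0.3-0.7 is a change SD of 0.9 to 2.1 drinks per day.

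**4. Contrasts that hold their level.** In the same calculation, the group term without an interaction stays at 5.0% at every change SD tried. So does an EFT-CET level comparison on the 28 intervention days with a random intercept, because the intercept then absorbs each person's change. Outcomes analysed at two visits are also safe: with one value per period, the residual already contains the variation in change.

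**5. Counts.** Over-dispersed counts were simulated (mean 5 per day, intercept SD 0.5 on the log scale, AR(1) day effect SD 0.4 with ρ 0.4; N = 52 or 76; 300-800 runs) and fitted by penalised quasi-likelihood. For the EFT-CET change test, random intercept plus AR(1) rejected 14-15% at a log-change SD of 0.2 and 26-28% at 0.35. Adding a random pre/post effect with N − 2 df gave about 4-7% throughout. For scale, if half the participants halve their drinking and half do not change, the log-change SD is ln 2/2 = 0.35.

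Two limits apply. The random-intercept fit already ran at 7-11% with no variation in change, so these rates overstate the part due to the missing term. The runs also do not settle the pre/post test: there the fit with the random effect (without day) rejected too often as well (8-10% at log SD 0.2, 39-49% at 0.5). The pre/post range above therefore rests on step 3 alone.

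**The case against.** The strongest reply is that neither document states the model examined here. The Protocol has the random effect without AR(1); the SAP has AR(1) without a named random effect or pre/post term. "A random effect" is not expressly limited to an intercept, and the SAP permits other correlation structures. The EFT-CET difference in change is not written as a model term; it is inferred from the endpoints and the sample-size section. All of this stands, and the defect is partly one of under-specification. It does not remove the problem: an intercept is the ordinary reading, and the SAP gives no trigger or named alternative for leaving AR(1). Taking the SAP alone is no safer. AR(1) without any random effect gives 1-8% for the change test but 26-34% for a level comparison on the intervention days (ρ 0.2 or 0.4).

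A second reply is that the SAP may intend only a comparison of levels during the intervention. On that reading the EFT-CET test is sound. But the SAP analyses breath samples over all five weeks in a manner similar to drinks, and Protocol 4.1 makes within-subject change an endpoint on its own.

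A reader might infer a definite false-positive rate, such as 10-25%, for both change tests, or conclude that every primary comparison is invalid. The documents support neither. They give no variance from which a rate follows, the pre/post test is less affected once day is in the model, and the contrasts in step 4 keep their level. Nor is the SAP's planned test of individual differences evidence of unexplained variation in change: it concerns moderation by AUDIT score, SES, age and gender.

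**Conclusion.** The concern holds conditionally. On the ordinary reading (random intercept plus AR(1)), no variance term carries person-to-person differences in change, so intervals for the pre/post change and for any EFT-CET difference in change are too narrow. If the change SD is 0.3-0.7 of the day-to-day SD, a nominal 5% test runs at about 8-26% for the EFT-CET change and about 7-17% for pre/post with linear day. With no variation in change both are 5%. These figures rest on assumed variances, complete 7 + 28 day records and a large-sample Gaussian approximation. The direction of the error depends only on participants differing in how much they change.

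**What to change.** In Protocol 5.2 and SAP Objective 1, for the daily outcomes:

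- Specify a participant random intercept plus a correlated participant random pre/post effect, and keep AR(1) for day-to-day dependence.
- Write the group-by-time term explicitly and name it as the EFT-CET test of change.
- Use person-level degrees of freedom (N − 2 for the EFT-CET contrast).
- State the fallback for non-convergence: ANCOVA of each person's intervention-period mean on the baseline-week mean for EFT-CET, and a person-level paired test for pre/post change.
- State whether pre/post change means average log change or change in average drinks. With a log link these differ once people change by different amounts.
- Apply the same structure to the BrAC model wherever a pre/post contrast is taken.

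The cost is wording and one added random effect with its covariance; no new data are needed. Intervals will be wider: in step 3 the true SE is about 1.1 to 1.75 times the model's at change SDs of 0.3-0.7. The model will occasionally fail to converge, which the fallback covers.

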6.0 Setting

6.1 *Describe the sites or locations where your research team will conduct the research. Consider each of the items listed below:*

- *Identify where your research team will identify and recruit potential subjects.*
- *Identify where the team will perform the research procedures.*
- *Describe the composition and involvement of any community advisory board(s).*
- *For research conducted in other locations, describe:*
 - *Site-specific regulations or customs affecting the research at those locations.*
 - *Local scientific and ethical review structure at those locations. Examples include work in other cultures or ethnic groups (within or outside of the U.S.) and work with churches. The HRPP will provide additional guidance for international research.*

Location of Recruitment:

Participants will be recruited from the Roanoke-Blacksburg community via posted flyers, word of mouth referrals, and electronic advertisements (e.g., Craigslist, Facebook). To the extent possible, we will attempt to minimize obstacles to participation. For example, travel barriers will be addressed by providing transportation or parking costs to participants, and scheduling barriers will be minimized by offering a flexible session schedule.

In addition, we will partner with BuildClinical to accelerate enrollment. BuildClinical is a data-driven platform that helps academic researchers recruit participants for research studies more efficiently using social media, software, and machine learning. They have worked with IRBs in the US to ensure adherence to all the appropriate guidelines and procedures. They utilize study-specific advertisements to engage participants on digital platforms such as Facebook, Google, WebMD, etc., and redirect them to a study-specific landing page should they click it. On the landing page, the person can complete an online pre-screen questionnaire that gets routed into BuildClinical's platform. BuildClinical's Secure Socket Layer (SSL) software, which encrypts all inputted information is HIPPA compliant and keeps potential participant information private.

Location of study:

All methods and measures will be conducted using standard operating procedures in the Addiction Recovery Research Center and [name] Laboratory at the Fralin Biomedical Research Institute at VTC. All staff (including recruitment staff) will be provided with cultural sensitivity training. We have a history of successful recruitment of drug and alcohol users. All participants will enroll on a voluntary basis and sign an IRB-approved consent form prior to study participation.

7.0 Study Intervention(s)/Investigational Agent(s)

7.1 Describe the study interventions (including behavioral interventions) and/or investigational agents (e.g., drugs or devices) to be used in this study. Consider each of the items listed below:

- *Drug/Device Handling: If the research involves drugs or devices, describe your plans to store, handle, and administer the drugs or devices so that they will be used only on subjects, and only by authorized investigators.*

- *Describe whether any of the following will be used: microwaves, X-rays, DEXA scans, general anesthesia, or sedation*
- *If control of the drugs or devices used in this protocol will be accomplished by following an established, approved organizational SOP (e.g., Research Pharmacy SOP for the Control of Investigational Drugs, etc.), please reference the SOP in this section.*

Episodic Future Thinking: Participants will generate positive future events they are looking forward to at a number of time points in the future (e.g., 1 day, 2 weeks, 1 month, 3 months, 1 year, 5 years, and 25 years) at S3 and S4. Participants will be reminded of these events using cues throughout the session and instructed to think about these cues as they make their decisions. These cues will be the cues texted to them over the monitoring phase. Questions about the cues (e.g., "How vivid is this cue to you, on a scale from 1-5", "How real does this cue feel to you, on a scale from 1-5", etc.) will be also texted to the participants together with the cues. This procedure is to ensure the participants are actually reading their cues when texted to them. A list of question examples is attached in the supporting documents.

Control Episodic Thinking: Participants will generate positive recent past events that have happened to them at a number of time points (last night from 7pm-10pm, yesterday between 4pm-7pm, yesterday between 1pm-4pm, yesterday from 10am-12pm, yesterday between 7am-10am, the night before last between 7pm-10pm, and evening before last between 4pm-7pm) at S3 and S4. Participants will be reminded of these events using cues throughout the session and instructed to think about these cues as they make their decisions. These cues will be the cues texted to them over the monitoring phase. Questions about the cues (e.g., "How vivid is this cue to you, on a scale from 1-5", "How real does this cue feel to you, on a scale from 1-5", etc.) will be also texted to the participants together with the cues. This procedure is to ensure the participants are actually reading their cues when texted to them. A list of question examples is attached in the supporting documents.

7.2 List the name of all drugs (including any vitamins, supplements, herbs, or nicotine) to be used in the study. Indicate whether they have FDA approval, and list any limitations for their use:

N/A

7.3 List all devices, how they will be used, their purpose in the study, and if they will be used in a manner consistent with their approved uses. If they

will be used in ways that are not yet FDA approved, indicate whether they need an IDE or a determination that they are exempt from the IDE Determination. If a determination of significant risk or non-significant risk is needed for any of the devices, include the researcher's recommendation for each of those devices:

We are using a device (BACtrack Mobile breathalyzer) that is under the purview of the FDA, but we have not and we believe we are not required to obtain an IDE from the FDA for the use of this device because it meets the requirements for IDE exempt in 21 CFR §812.2(c)(3).

These requirements are as follows:

(3) A diagnostic device, if the sponsor complies with applicable requirements in 809.10(c) and if the testing:

- (i) Is noninvasive,
- (ii) Does not require an invasive sampling procedure that presents significant risk,
- (iii) Does not by design or intention introduce energy into a subject, and
- (iv) Is not used as a diagnostic procedure without confirmation of the diagnosis by another, medically established diagnostic product or procedure.

Our use of this device is noninvasive, does not require an invasive sampling procedure that presents sufficient risk, does not by design or intention introduce energy into a subject, and is not used as a diagnostic procedure without confirmation of the diagnosis by another procedure. Regarding point (iv) specifically, the only diagnosis under consideration in our study is alcohol use disorder, but we are not using the device to diagnose this disorder. We are using other established questionnaires and assessments as uploaded to the IRB to assess whether someone has the symptoms of alcohol use disorder, and the breathalyzer device is only being used to monitor ongoing alcohol use. Ongoing alcohol use by itself is not sufficient to diagnose alcohol use disorder and we are not using it for this purpose. Instead, we are periodically readministering behavioral diagnostic surveys to determine if incidence of alcohol use disorder symptoms change throughout the study.

The BACtrack Mobile breathalyzer is FDA cleared but confidential, which is why it does not appear in a search. The 510(k) number is regulated confidentially, but the listing number is D085312 and the premarket submission number is K090067. Additionally, the

EPISODIC THINKING AND ALCOHOL USE IRB 22-358

BACtrack Mobile is not approved to treat or diagnose a disease, but we do not intend to use it for this purpose. The use of the BACtrack Mobile is non-diagnostic in this study but accurate enough to measure BAC remotely.

The team will be using the BACtrack Mobile for this protocol. The 510(k) number (i.e., K090067) is the same as the other model and this information is confidential. Our contact at BACtrack confirmed that the device is FDA cleared and also provided the below and attached information.

Attached you will find a review from [Counterpoint Journal](#), which compares BACtrack Mobile to police and industrial/DOT handheld units: <https://www.counterpoint-journal.com/>

Additionally, here's a link to an abstract from researchers at the Perelman School of Medicine at the University of Pennsylvania. While BACtrack performed best relative to a police-grade breathalyzer (the Intoxilyzer 240), we've also been informed BACtrack outperformed the Intoxilyzer 240 when comparing BAC results to a blood test.

http://injuryprevention.bmj.com/content/23/Suppl_1/A15.1

Additionally, here are media reviews of BACtrack Mobile compared to police units:

<https://well.blogs.nytimes.com/2015/12/21/turning-your-smartphone-into-a-breathalyzer/>

<https://www.nbclosangeles.com/investigations/Do-It-Yourself-Breathalyzers-368687801.html>

Functional magnetic resonance imaging (fMRI) is a technique that noninvasively measures correlates of neural activity (Ogawa et al., 1992) and allows the identification of cerebral substrates associated with processes that shape human awareness and perception, such as visual, auditory, emotional, somatosensory. Unlike positron emission tomography (PET), fMRI does not require the injection of intravenous tracers or exposure of the subject to any ionizing radiation. Another advantage of fMRI is that multiple scans can be obtained in a single (or multiple) imaging session(s), which allows for acquisition of 1000 scans over a few minutes, while a PET study is limited to 16 scans over 2 hours (Friston et al., 1995; Buckner et al., 1996). Thus, fMRI allows us to capitalize on increased temporal resolution and repetition of conditions capabilities in an effort to study brain function.

The MRI scanner we will use has a magnetic field of approximately 3.0T. Scanners with a 3.0T field strength have been approved for clinical use by the FDA and are currently available for routine clinical applications.

The MRI imaging experiments will be performed on a Siemens 3T scanner, and we will only use structural and functional sequences that conform to FDA guidelines for specific absorption rate (SAR) of radio frequency energy. SAR is limited by both hardware and

software checks on the MRI scanners. A standard head coil will be used to collect the MR data.

The hCG Urine Pregnancy Test Cassettes is a test kit for the determination of hCG (Human Chorionic Gonadotropin) in urine specimens. This test kit is used to obtain a visual qualitative result for early detection of pregnancy. These tests are Standardized with WHO International Reference Standard and FDA Cleared & CLIA Waived.

The QuickTox 5-panel drug test dip card delivers results within 5 minutes. The QuickTox is FDA-approved and CLIA-Waived. The 5-panel test detects benzodiazepines, marijuana, opiates, meth, and cocaine.

7.4 If the drug is investigational (has an IND) or the device has an IDE or a claim of abbreviated IDE (non-significant risk device), include the following information:

- *Identify the holder of the IND/IDE/abbreviated IDE.*
- *Explain procedures followed to comply with sponsor requirements for FDA regulated research for the following:*

	Applicable to:		
FDA Regulation	IND Studies	IDE studies	Abbreviated IDE studies
21 CFR 11	X	X	
21 CFR 54	X	X	
21 CFR 210	X		
21 CFR 211	X		
21 CFR 312	X		
21 CFR 812		X	X
21 CFR 820		X	

N/A

